5.3 SCREEN FAILURES

Screen failures are defined as patients who consent to participate in the clinical trial but are not subsequently randomly assigned to the study intervention or are not included in the registry if not eligible to be randomized. A minimal set of screen failure information is required to ensure transparent reporting of screen failure patients, to meet the Consolidated Standards of Reporting Trials (CONSORT) publishing requirements and to respond to queries from regulatory authorities. Minimal information includes demography, screen failure details (demographics, reasons for no enrollment including eligibility criteria) .

Individuals who do not meet the criteria for participation in this trial (screen failure) because of a modifiable exclusion criterion may be rescreened patient

5.4 STRATEGIES FOR RECRUITMENT AND RETENTION

The Clinical Coordinating Center (CCC) will review DCC-generated weekly data reports on screening and enrollment and actively reach out to sites on a regular basis, with emphasis on volume of enrollment but also sex-specific and racial/ethnic minority targets for enrollment. A separate detailed recruitment and retention plan will be specified in the manual of procedures (MOP) and site-specific plans will be included in a site-specific standard operating procedure (SOP).

The Data Coordinating Center (DCC) will aid the process of screening and recruitment of eligible patients by issuing weekly data reports on the cadence of screening and enrollment, as well as patient retention. These reports will summarize the number of patients screened and the percent of patients randomized at each site and the reasons for screen failure. Demographic characteristics of screened and randomized patients will be reported to keep track of the cohort characteristics and to encourage enrollment of diverse populations. These reports will inform discussion of strategies to overcome enrollment obstacles unique to each site.

6.0 STUDY INTERVENTION

6.1 STUDY INTERVENTION(S) ADMINISTRATION

6.1.1 Study Intervention Description

The study intervention(s) (TAVR vs SAVR) are standard of care procedures performed with FDA-approved commercially available devices. Time between randomization and planned date of intervention should be 2 weeks or less.

6.2 MEASURES TO MINIMIZE BIAS: RANDOMIZATION

Patients will be randomized 1:1 to TAVR or SAVR using a centralized, secure web-based randomization system managed by the Data Coordinating Center, employing permuted blocks with varying block sizes and stratified by: (1) sex and (2) low or intermediate/high SAVR (clinical) risk and (3) planned TAVR type (in the event of randomization to TAVR). This is an open-label study; patients, treating clinicians, and site staff will not be blinded to treatment assignment. Randomization will be adaptive to maintain balance in study arm allocation within each site.

6.2.1 Risk Strata Definitions and Examples

6.2.1.1 Overview

To apply the trial equipoise requirement consistently, each patient will be assigned two independent strata by the **Patient Selection Committee**:

1. **SAVR Clinical Risk Stratum** (operative risk based on clinical factors and STS score), and

2. TAVR Anatomic/Procedural Risk Stratum (transcatheter risk based primarily on CT anatomy/access).

Strata are based on objective inputs (e.g., STS-PROM, CT measurements) plus committee judgment. Final classifications are documented in the committee review record.

6.2.1.2 SAVR Clinical Risk Strata

Low SAVR risk: STS-PROM typically <3% and no major modifiers expected to materially increase operative risk.

Intermediate SAVR risk: STS-PROM typically 3–8%, or STS-PROM <3% with **one major modifier**.

High SAVR risk: STS-PROM typically >8%, or ≥2 major modifiers, or committee determination of substantially elevated operative risk.

Prohibitive/Extreme SAVR risk (not eligible): STS-PROM typically ≥15% or SAVR deemed unreasonable/unsafe.

Major SAVR modifiers (examples): severe frailty/limited mobility, oxygen-dependent lung disease, severe pulmonary hypertension, dialysis/advanced CKD, advanced liver disease, hostile chest (redo sternotomy, radiation), porcelain aorta, prior CABG with high re-entry risk, other major organ dysfunction.

6.2.1.3 TAVR Anatomic/Procedural Risk Strata

Low TAVR risk: transfemoral access feasible with acceptable vascular features; anatomy within device ranges; no high-risk coronary/root features; bicuspid morphology/calcification pattern favorable.

Intermediate TAVR risk: feasible transfemoral access with borderline vascular features and/or borderline root/coronary features and/or moderate bicuspid risk features; may require routine mitigation strategies.

High TAVR risk: anatomy/access expected to materially increase major complication or technical failure risk (e.g., high coronary obstruction risk requiring protection strategy, severe bulky/asymmetric raphe/leaflet or LVOT calcification with underexpansion/PVL/annular injury concern, high-risk access).

Prohibitive/Extreme TAVR risk (not eligible): TAVR deemed unreasonable/unsafe due to access/anatomic constraints not amenable to mitigation.

6.2.1.4 Equipoise rule and examples

Patients are eligible for randomization only if **TAVR and SAVR strata differ by no more than one level** and neither approach is **prohibitive**.

- **Allowed:** Low vs Intermediate; Intermediate vs High
- **Not allowed:** Low vs High
- **Not allowed:** Any Prohibitive designation

Examples:

- Low SAVR + Intermediate TAVR → Eligible
- Low SAVR + High TAVR → Not eligible
- High SAVR + Intermediate TAVR → Eligible

- Prohibitive SAVR or Prohibitive TAVR → Not eligible

6.3 PATIENT SELECTION COMMITTEE: ELIGIBILITY ADJUDICATION AND EQUIPOISE DETERMINATION

A centralized PSC will confirm clinical equipoise and adjudicate final eligibility prior to randomization to ensure consistent application of inclusion/exclusion criteria and risk stratification across sites. Details will be specified in the PSC charter and MOP.

6.4 STUDY INTERVENTION COMPLIANCE

Site documentation will be kept and maintained and reviewed in line with the MOP.

7 STUDY INTERVENTION DISCONTINUATION AND PATIENT DISCONTINUATION/WITHDRAWAL

7.1 FAILURE OF PATIENT TO UNDERGO RANDOMIZED TREATMENT ASSIGNMENT

Failure for a patient to undergo the randomized treatment assignment does not mean discontinuation from the study, and remaining study procedures should be completed as indicated by the study protocol. If a clinically significant finding is identified (including but not limited to changes from baseline) after randomization, the investigator or qualified designee will determine if any change in patient management is needed. Any new clinically relevant finding will be reported as an adverse event (AE).

The data to be collected pertaining to this eventuality will include the following: Documentation for reasons for deviation from randomized intervention (including cross over or decision for no intervention).

7.2 PATIENT WITHDRAWAL FROM THE STUDY

Patients are free to withdraw from participation in the study at any time.

An investigator may discontinue or withdraw a patient from the study for the following reasons:

- Significant study intervention non-compliance
- If any clinical adverse event (AE), laboratory abnormality, or other medical condition or situation occurs such that continued participation in the study would not be in the best interest of the patient

The reason for patient discontinuation or withdrawal from the study will be recorded on the Case Report Form (CRF) specified in the MOP.

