4.3 END OF STUDY DEFINITION

A patient is considered to have completed participation in the study if he or she has completed all phases of the study including the last visit or the last scheduled procedure shown in the Schedule of Activities (SoA), Section 1.3, or has withdrawn from the study. The determination of loss to follow-up will not be made until the end of the study. The end of the study is defined as 10 years (+ or - 45 days) following the randomization of the 1200th patient.

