8.10 ADVERSE EVENTS AND SERIOUS ADVERSE EVENTS

8.10.1 Definition of Adverse Events and Reportable Adverse Events for the BELIEVERS trial

An adverse event (AE) is any untoward medical occurrence associated with the use of an intervention, whether or not considered intervention related. Given this study is comparing commercially approved devices, reportable AEs for the BELIEVERS trial will be **restricted to those AEs (both serious and non-serious) corresponding to the study's primary, secondary and safety endpoints derived directly from site reporting** (table 1); those primary, secondary, safety and exploratory endpoints derived from echocardiography or CT corelabs will be reported directly to the DCC by the respective corelabs.

Other reportable AEs complications that can occur include clinical or subclinical valve thrombosis, bioprosthetic valve failure, valve reintervention, valve or heart-failure related hospitalization. Additional details on events that will require reporting will be specified in the MOP and specific guidance in this regard will be provided by the CCC to the sites on site initiation and to the CEC.

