8.10.5 Adverse Event Reporting

All relevant AEs and SAEs (as defined in VARC-3) will be captured from the time of randomization until the study patient's participation has ended (i.e., completion of study or withdrawal of consent), time period as specified above.

Adverse events must be followed until resolution, stabilization, or study completion. The AE and/or SAE should be reported to the sponsor, and CRF Forms completed **as soon as possible but no later than 10 working days of awareness**.

This study uses standard-of-care procedures and FDA-approved, commercially available devices. Therefore, IRB reporting will follow institutional and local IRB requirements for AEs/SAEs, and endpoint clinical events will additionally be captured and adjudicated by the CEC throughout follow-up as specified in the protocol

and MOP.

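### Section 7.2 lets an unblinded investigator withdraw a patient from the study for an adverse event, so collection of non-fatal endpoints and KCCQ can stop because of outcome, and 4.3 then counts that patient as having completed

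*Protocol*

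**What the plan says.** All references are to the protocol.

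- **7.2, power to withdraw.** "An investigator may discontinue or withdraw a patient from the study for the following reasons". The act is withdrawal from the study, not from a visit or a test. The second listed reason begins "If any clinical adverse event (AE), laboratory abnormality, or other medical condition or situation occurs such that continued participation" and turns on whether, in the investigator's judgement, a "situation occurs such that continued participation in the study would not be in the best interest of the patient".
- **8.10.1, what an adverse event is here.** Reportable events are restricted to those matching the "primary, secondary and safety endpoints derived directly from site reporting". Endpoints read by the core laboratories go directly to the data coordinating center.
- **4.3, completion.** A patient has completed participation on finishing the last visit "or the last scheduled procedure shown in the Schedule of Activities (SoA), Section 1.3, or has withdrawn from the study".
- **8.10.5, capture window.** Events are captured until participation has ended, glossed as "i.e., completion of study or withdrawal of consent".
- **7.4, partial withdrawal.** Best efforts are promised on vital status for every randomized patient. Unless the patient explicitly withdraws consent for data collection, limited further information may be gathered. The items named are vital status, date of death and location of care.
- **4.1 and 6.2.** The trial is open-label for patients, clinicians and site staff.
- **9.4.2 and 9.4.8.** Pairs are compared over the follow-up they share. Patients without an event are censored at last known contact. A patient with no KCCQ at one year or later is non-evaluable on that tier.

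**The concern.** The intervention is one procedure. After it, the study asks for mostly standard-of-care follow-up plus questionnaires and functional tests (8.8). Withdrawing a patient from the study therefore stops no study treatment. What it can stop is the recording of outcomes.

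Because the adverse events the trial collects are largely its endpoints, 7.2 allows an endpoint event to be the reason why later endpoints go unrecorded, and the person deciding knows the arm. A patient withdrawn after a qualifying rehospitalization (tier 5) might have no later stroke or reintervention on record. One withdrawn before a year has no evaluable KCCQ on tier 6. In the key secondary endpoint, missing KCCQ is imputed from a mixed model with arm, visit and a subject effect (9.4.8). That model has no term for the event that led to withdrawal.

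The completion rule adds a reporting problem. By 4.3 the withdrawn patient is a completer, and by 7.3 is not lost to follow-up as long as vital status is known. Neither label shows that the non-fatal endpoints are missing.

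**Working it through.** **1. The clauses side by side.**

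| Question | Answer in the protocol |
|---|---|
| Can an adverse event end participation by the investigator's decision? | Yes, at discretion (7.2) |
| Are those events endpoints? | Largely (8.10.1) |
| Is the withdrawn patient a completer? | Yes (4.3) |
| Does event capture then stop? | Unclear. 8.10.5 names study completion and withdrawal of consent. An investigator's withdrawal is not the second, but 4.3 makes it a form of the first |
| Is death still ascertained? | Yes, best efforts for all randomized patients (7.4) |
| Are stroke, reintervention, adjudicated rehospitalization and KCCQ still collected? | Not named in 7.4, where further collection is optional and limited |
| Does 7.4 cover withdrawal by the investigator? | Not addressed. It describes patients who choose to reduce visits |

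Section 7.1 points the other way from 7.2: not receiving the assigned treatment does not end participation, and a significant finding after randomization prompts a review of management and an adverse event report.

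**2. The plan's own power figure.** Inputs from 9.2, Table 2 and 9.4.1: most-severe-event rates for SAVR of 5.3, 1.1, 3.0, 1.7, 9.3 and 5.0% (total 25.4%) and for TAVR of 7.1, 1.5, 4.0, 2.3, 12.5 and 6.7% (total 34.1%); 510 patients per arm with complete 3-year data; two-sided 5% Finkelstein-Schoenfeld test. Simulating as 9.4.1 describes (independent exponential times for five clinical tiers, binary KCCQ, 10,000 trials) gives 85.4%, against 85.3% stated. The model reproduces the plan.

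**3. Stress test.** The documents give no withdrawal rate. As a deliberately heavy assumption, 50% of patients with a first non-fatal tier event are withdrawn at that event, which is about 8% of SAVR and 10 to 11% of TAVR patients. The triggering event counts; later non-fatal events and KCCQ are lost. There are 400 trials per row, and the win ratio is above 1 when SAVR does better. Power is Φ(mean Z − 1.96), with a standard error of about 0.05 on mean Z.

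| Withdrawn | Deaths | Mean Z | Win ratio | Power |
|---|---|---|---|---|
| none | all seen | 2.95 | 1.41 | 84% |
| both arms | kept | 2.97 | 1.42 | 84% |
| both arms | lost | 3.01 | 1.42 | 85% |
| SAVR only | kept | 2.76 | 1.38 | 79% |
| SAVR only | lost | 2.66 | 1.37 | 76% |
| TAVR only | lost | 3.32 | 1.48 | 91% |

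With no true difference (TAVR rates in both arms), SAVR-only withdrawal moves the win ratio from 1.00 to 0.98 with deaths kept and 0.96 with deaths lost. TAVR-only withdrawal with deaths lost gives 1.04.

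**4. Reading.** Equal withdrawal changes nothing beyond simulation error. Unequal withdrawal shifts the estimate against the arm that loses patients: the triggering event still counts against the withdrawn patient, while the shortened shared window hides the comparator's later events. Keeping deaths, as 7.4 intends, reduces the shift.

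**The case against.** The case for leaving the text alone has real force.

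- **7.4 reaches further than a quick reading suggests.** Its vital-status promise covers all randomized patients, only explicit withdrawal of consent ends all collection, and its list of items is introduced as inclusive rather than complete. A reader might infer that 7.2 also cuts off deaths. The documents do not support that: the top tier of both win-ratio endpoints is protected in intent. This stands.
- **8.10.5 does not list the investigator's decision** as an end of capture, and 9.3 keeps partially withdrawn patients in the intention-to-treat set. This stands, but it leaves 4.3 and 8.10.5 open to two readings.
- **The clause is discretionary.** An endpoint alone does not meet it. With mostly routine follow-up remaining, it should seldom be met.
- **Size.** A reader might count every patient whose worst Table 2 event is a non-fatal clinical one as at risk: 600 × 15.1% + 600 × 20.3% ≈ 212. That count is not usable. Table 2 classifies by most severe event, so the rehospitalization tier, 600 × 9.3% + 600 × 12.5% ≈ 131 of them, has by construction no higher-tier event to lose. Under the plan's independent event times, even an assumed 5 to 10% withdrawal after a first non-fatal event would cost roughly one patient in the whole trial a later higher-tier event, and fewer with deaths kept.
- **Direction.** A reader might infer a pull toward no difference because the worse arm has more events. The stress test does not show it: equal withdrawal has no visible effect, and TAVR-only withdrawal moves the result away from no difference.
- **Disposition.** 7.2 requires the reason for withdrawal on the case report form, and 9.4.8 summarizes missing data by arm and visit. Nothing says the tables will pool withdrawals with completers. The fault is in the 4.3 definition, not in a stated reporting plan.

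What survives is the stated permission in 7.2, the wrong completion definition in 4.3, and the silence of 7.4 on the non-fatal endpoints after an investigator's withdrawal.

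**Conclusion.** The point holds as a defect in stated rules, with a probably small effect. The protocol permits outcome-dependent loss of tiers 2 to 6 and of KCCQ in the key secondary endpoint, in an open-label trial where leaving the study removes no treatment, and it labels those patients complete. Deaths are protected by 7.4.

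The bias could favor either arm and needs withdrawal to differ between arms. The range of 1.37 to 1.48 around 1.41 rests on an assumed 50% withdrawal at the first non-fatal event, in one arm only, with deaths also lost. It is a bound for illustration, not a forecast. The simulation takes event times as independent. If later events cluster in patients who have already had one, more would be lost, but the documents give no correlation. The correction is worth making because it is cheap and the present wording works against the stated aim of 7.4 to limit loss of outcome data.

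**What to change.** These changes concern data collection only.

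- **7.2, second reason.** Replace it with wording to this effect: the investigator may stop individual study-specific assessments for the patient's welfare; the patient stays in the study and endpoint follow-up continues by visit, remote contact or records; only the patient's own withdrawal of consent for data collection ends follow-up.
- **7.4.** Name disabling and non-disabling stroke, valve reintervention, adjudicated rehospitalization and, where the patient is willing, KCCQ as continuing after any withdrawal short of withdrawn consent, whoever initiated it.
- **4.3.** Delete "or has withdrawn from the study" from the completion definition and report such patients as not completing, so that 4.3 agrees with 7.1, 7.4 and 8.10.5.

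The cost is an amendment to the wording and a few more patients followed by records or telephone. Clinical care is unaffected.

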7.3 LOSS TO FOLLOW-UP

A patient will be considered lost to follow-up (LTF) will be ascertained at the time of the last study visit as per protocol, if the patient survival status cannot be determined and the patient is unable to be contacted by the study site staff.

The following actions must be taken if a patient fails to return to the clinic for a required study visit:

- The site will attempt to contact the patient and reschedule the missed visit within the manual of operations (MOP)- specified time frame and counsel the patient on the importance of maintaining the assigned visit schedule and ascertain if the patient wishes to and/or should continue in the study.
- Before a patient is deemed lost to follow-up, the investigator or designee will make every effort to regain contact with the patient (up to study completion). These contact attempts should be documented in the patient's medical record or study file.

7.4 PARTIAL WITHDRAWAL

To minimize loss of outcome information and preserve the integrity of long-term follow-up, the study team will make best efforts to ascertain vital status for all randomized patients through the end of study follow-up, even if a patient withdraws from in-person visits. Patients may choose to discontinue study visits and/or complete only remote follow-up; however, unless a patient explicitly withdraws consent for any further data collection, the study may continue to collect limited follow-up information including vital status (alive/deceased), date of death (if applicable), and location of care (in hospital or at home).

Vital status ascertainment may include review of the electronic health record and health system administrative data, contact with the patient or a designated proxy/emergency contact, communication with treating clinicians, and review of publicly available sources or applicable mortality databases, consistent with local regulations and IRB approvals. All attempts to contact the patient or proxy and all sources used for vital status determination will be documented. If a patient explicitly withdraws consent for all further data collection, no additional contact will be made and only data collected prior to withdrawal will be retained and analyzed as permitted by applicable regulations and IRB policy.

8 STUDY ASSESSMENTS AND PROCEDURES

8.1 SCREENING/BASELINE

The following screening and baseline assessments should be conducted within 90 days of index procedure, unless otherwise noted. All assessments marked with an asterisk (*) are required prior to the patient selection committee.

- Signed Informed Consent*
- Demographics and Medical History*
- Physical Exam and vital signs*
- STS risk score and EuroSCORE II*
- SYNTAX score only in the presence of coronary artery disease requiring intervention*
- Concomitant Cardiovascular Medications*
- NIH Stroke Scale (NIHSS) and Modified Rankin Scale (mRS)
- Laboratory Test (Complete Blood Count, Comprehensive Metabolic Panel, and NT-proBNP). Sites who do not have the capability to collect an NT-proBNP lab, a BNP lab will be accepted instead *
- Pregnancy test (only for women of childbearing potential)
- Pulmonary Function Test (PFT) only for patients with a history of severe lung disease
- 12-lead ECG*
- Transthoracic Echocardiogram (TTE)*
- NYHA classification and CCS angina*
- 6 min walk test
- Frailty index (ADLs, 5 Meter Walk Test, and Grip Strength)*
- Kansas City Cardiomyopathy Questionnaire (KCCQ)
- SF-12 Questionnaire
- QOR-15 scale (Quality of recovery)
- PHQ-9 scale (Depression score)
- 3D Cardiac contrast CT within 1 year of case review committee date. If a TEE or a cardiac MRI are available per standard of care within 6 months of the patient selection committee date, the images will be collected for the study. *
- Iliofemoral CT Angiography within 1 year of case review committee date*
- Invasive or CT coronary Angiography within 1 year of case review committee date*
- Patient Selection Committee will be scheduled after completion of all of the above assessments marked with an asterisk (*)

